11.13.6. Efficacy Figures

Efficacy Figures					
No.	Population	IDSL / TST ID / Example Shell	Title	Programming Notes	Deliverable [Priority]
Gas transfer measure					
2.01	Analysis	Non-Standard EFF_F1	Spaghetti Plot of DLco	DLco has measures at Baseline, Day 4, Day 5, and Day 7 for each period as well as screening and follow-up. Includes pre/post exercise and saline challenge.	SAC [2]
2.02	Analysis	Non-Standard EFF_F22	Spaghetti Plot of DLco by Site	DLco has measures at Baseline, Day 4, Day 5, and Day 7 for each period. Excludes post exercise and post saline challenge.	SAC [2]
2.03	Analysis	Non-Standard EFF_F2	Mean (95% CI) Plot of DLco	Create this graph twice, one graph with Mayo patients and another graph with Hennepin patients	SAC [2]
2.04	Analysis	Non-Standard EFF_F3	Mean (95% CI) Plot of Chronic DLco	Create this graph twice, one graph with Mayo patients and another graph with Hennepin patients	SAC [2]
2.05	Analysis	Non-Standard EFF_F4	Plot of DLco by Individual and Treatment	DLco has measures at Baseline, Day 4, Day 5, and Day 7 for each treatment as well as screening and follow-up. Includes pre/post exercise and saline challenge. Horizontal line represents baseline values	SAC [2]
2.06	Analysis	Non-Standard EFF_F5	Plot of Change from Baseline for Chronic DLco by Individual and Treatment	Only pre-challenge DLco values	SAC [2]

Efficacy Figures					
No.	Population	IDSL / TST ID / Example Shell	Title	Programming Notes	Deliverable [Priority]
2.07	Analysis	Non-Standard EFF_F6	Mean (95% CI) Plot of DLco Change from Baseline	
DLco has means at Baseline, Day 4, Day 5, and Day 7 for each treatment and includes pre/post exercise and saline challenge. Baseline is minus day -1 for exercise and no challenge, but should be calculated as post minus pre for Saline.
 
Create this graph twice, one graph with Mayo patients and another graph with Hennepin patients
	SAC [2]
2.08	Analysis	Non-Standard EFF_F7	Mean (95% CI) Plot of Exercise DLco	
DLco has measures at Baseline and Day 7 for each treatment and a follow-up. Graph should include pre/post exercise values.
 
Create this graph twice, one graph with Mayo patients and another graph with Hennepin patients
	SAC [2]
2.09	Analysis	Non-Standard EFF_F8	Mean (95% CI) Plot of Change from Exercise for DLco	
DLco has means at Baseline and Day 7 for each treatment and a follow-up. The bars represent the mean change from just prior to exercise to post exercise. mean(Post-Pre)
 
Create this graph twice, one graph with Mayo patients and another graph with Hennepin patients
	SAC [2]
2.10	Analysis	Non-Standard EFF_F9	Mean (95% CI) Plot of Percent Change from Exercise for DLco	
DLco has means at Baseline and Day 7 for each treatment and a follow-up. The bars represent the mean percent change from just prior to exercise to post exercise.
 
Create this graph twice, one graph with Mayo patients and another graph with Hennepin patients
	SAC [2]

Efficacy Figures					
No.	Population	IDSL / TST ID / Example Shell	Title	Programming Notes	Deliverable [Priority]
2.11	Analysis	Non-Standard EFF_F10	Mean (95% CI) Plot of Percent Change from Saline for DLco	DLco has means at Day 5 for each treatment and a follow-up. The bars represent the mean percent change from just prior to exercise to post saline infusion. Create this graph twice, one graph with Mayo patients and another graph with Hennepin patients	SAC [2]
2.12	Analysis	Non-Standard EFF_F24	Bar Plot of Saline Challenge for DLco by Subject	Bars should be able to distinguish pre- and post-saline values. On the bars for each patient should be text. The text is the difference between before and after and the percent change, as seen in the mock up Create this graph twice, one graph with Mayo patients and another graph with Hennepin patients	SAC [2]
2.13	Analysis	Non-Standard EFF_F1	Spaghetti Plot of DLno	DLno has measures at Baseline, Day 4, Day 5, and Day 7 for each period as well as screening and follow-up. Includes pre/post exercise and saline challenge.	SAC [2]
2.14	Analysis	Non-Standard EFF_F2	Mean (95% CI) Plot of DLno		SAC [2]
2.15	Analysis	Non-Standard EFF_F3	Mean (95% CI) Plot of Chronic DLno		SAC [2]
2.16	Analysis	Non-Standard EFF_F4	Plot of DLno by Individual and Treatment	DLno has measures at Baseline, Day 4, Day 5, and Day 7 for each treatment as well as screening and follow-up. Includes pre/post exercise and saline challenge. Horizontal line represents baseline values	SAC [2]
2.17	Analysis	Non-Standard EFF_F5	Plot of Change from Baseline for Chronic DLno by Individual and Treatment	Only pre-challenge DLno values	SAC [2]

Efficacy Figures					
No.	Population	IDSL / TST ID / Example Shell	Title	Programming Notes	Deliverable [Priority]
2.18	Analysis	Non-Standard EFF_F6	Mean (95% CI) Plot of DLno Change from Baseline	DLno has means at Baseline, Day 4, Day 5, and Day 7 for each treatment and includes pre/post exercise and saline challenge. Baseline is minus day -1 for exercise and no challenge, but should be calculated as post minus pre for Saline.	SAC [2]
2.19	Analysis	Non-Standard EFF_F7	Mean (95% CI) Plot of Exercise DLno	DLno has measures at Baseline and Day 7 for each treatment and a follow-up. Graph should include pre/post exercise values.	SAC [2]
2.20	Analysis	Non-Standard EFF_F8	Mean (95% CI) Plot of Change from Exercise for DLno	DLno has means at Baseline and Day 7 for each treatment and a follow-up. The bars represent the mean change from just prior to exercise to post exercise. mean(Post-Pre)	SAC [2]
2.21	Analysis	Non-Standard EFF_F9	Mean (95% CI) Plot of Percent Change from Exercise for DLno	DLno has means at Baseline and Day 7 for each treatment and a follow-up. The bars represent the mean percent change from just prior to exercise to post exercise.	SAC [2]
2.22	Analysis	Non-Standard EFF_F10	Mean (95% CI) Plot of Percent Change from Saline for DLno	DLno has means at Day 5 for each treatment and a follow-up. The bars represent the mean percent change from just prior to exercise to post saline infusion.	SAC [2]
2.23	Analysis	Non-Standard EFF_F24	Bar Plot of Saline Challenge for DLno by Subject	Bars should be able to distinguish pre- and post-saline values. On the bars for each patient should be text. The text is the difference between before and after and the percent change, as seen in the mock up Create this graph twice, one graph with Mayo patients and another graph with Hennepin patients	SAC [2]
2.24	Analysis	Non-Standard EFF_F1	Spaghetti Plot of D _M	D _M has measures at Baseline, Day 4, Day 5, and Day 7 for each period as well as screening and follow-up. Includes pre/post exercise and saline challenge.	SAC [2]

Efficacy Figures					
No.	Population	IDSL / TST ID / Example Shell	Title	Programming Notes	Deliverable [Priority]
2.25	Analysis	Non-Standard EFF_F2	Mean (95% CI) Plot of D_M		SAC [2]
2.26	Analysis	Non-Standard EFF_F3	Mean (95% CI) Plot of Chronic D_M		SAC [2]
2.27	Analysis	Non-Standard EFF_F4	Plot of D_M by Individual and Treatment	D_M has measures at Baseline, Day 4, Day 5, and Day 7 for each treatment as well as screening and follow-up. Includes pre/post exercise and saline challenge. Horizontal line represents baseline values	SAC [2]
2.28	Analysis	Non-Standard EFF_F5	Plot of Change from Baseline for Chronic D_M by Individual and Treatment	Only pre-challenge D_M values	SAC [2]
2.29	Analysis	Non-Standard EFF_F6	Mean (95% CI) Plot of D_M Change from Baseline	D_M has means at Baseline, Day 4, Day 5, and Day 7 for each treatment and includes pre/post exercise and saline challenge. Baseline is minus day -1 for exercise and no challenge, but should be calculated as post minus pre for Saline.	SAC [2]
2.30	Analysis	Non-Standard EFF_F7	Mean (95% CI) Plot of Exercise D_M	D_M has measures at Baseline and Day 7 for each treatment and a follow-up. Graph should include pre/post exercise values.	SAC [2]
2.31	Analysis	Non-Standard EFF_F8	Mean (95% CI) Plot of Change from Exercise for D_M	D_M has means at Baseline and Day 7 for each treatment and a follow-up. The bars represent the mean change from just prior to exercise to post exercise. mean(Post-Pre)	SAC [2]
2.32	Analysis	Non-Standard EFF_F9	Mean (95% CI) Plot of Percent Change from Exercise for D_M	D_M has means at Baseline and Day 7 for each treatment and a follow-up. The bars represent the mean percent change from just prior to exercise to post exercise.	SAC [2]

Efficacy Figures					
No.	Population	IDSL / TST ID / Example Shell	Title	Programming Notes	Deliverable [Priority]
2.33	Analysis	Non-Standard EFF_F10	Mean (95% CI) Plot of Percent Change from Saline for D_M	D_M has means at Day 5 for each treatment and a follow-up. The bars represent the mean percent change from just prior to exercise to post saline infusion.	SAC [2]
2.34	Analysis	Non-Standard EFF_F1	Spaghetti Plot of V_c	V_c has measures at Baseline, Day 4, Day 5, and Day 7 for each period as well as screening and follow-up. Includes pre/post exercise and saline challenge.	SAC [2]
2.35	Analysis	Non-Standard EFF_F2	Mean (95% CI) Plot of V_c		SAC [2]
2.36	Analysis	Non-Standard EFF_F3	Mean (95% CI) Plot of Chronic V_c		SAC [2]
2.37	Analysis	Non-Standard EFF_F4	Plot of V_c by Individual and Treatment	V_c has measures at Baseline, Day 4, Day 5, and Day 7 for each treatment as well as screening and follow-up. Includes pre/post exercise and saline challenge. Horizontal line represents baseline values	SAC [2]
2.38	Analysis	Non-Standard EFF_F5	Plot of Change from Baseline for Chronic V_c by Individual and Treatment	Only pre-challenge V_c values	SAC [2]
2.39	Analysis	Non-Standard EFF_F6	Mean (95% CI) Plot of V_c Change from Baseline	V_c has means at Baseline, Day 4, Day 5, and Day 7 for each treatment and includes pre/post exercise and saline challenge. Baseline is minus day -1 for exercise and no challenge, but should be calculated as post minus pre for Saline.	SAC [2]
2.40	Analysis	Non-Standard EFF_F7	Mean (95% CI) Plot of Exercise V_c	V_c has measures at Baseline and Day 7 for each treatment and a follow-up. Graph should include pre/post exercise values.	SAC [2]

Efficacy Figures					
No.	Population	IDSL / TST ID / Example Shell	Title	Programming Notes	Deliverable [Priority]
2.41	Analysis	Non-Standard EFF_F8	Mean (95% CI) Plot of Change from Exercise for Vc	Vc has means at Baseline and Day 7 for each treatment and a follow-up. The bars represent the mean change from just prior to exercise to post exercise. mean(Post-Pre)	SAC [2]
2.42	Analysis	Non-Standard EFF_F23	Forest Plot of DL End Points Change	Forest plot of DLco, DLno, Vc, and Dm change from baseline to day 7, change from pre and post saline for DLco and change from pre/post exercise on day 7 for DLco. Include the mean absolute change next to the box plot as seen in the mock-up	SAC[2]
2.43	Analysis	Non-Standard EFF_F9	Mean (95% CI) Plot of Percent Change from Exercise for Vc	Vc has means at Baseline and Day 7 for each treatment and a follow-up. The bars represent the mean percent change from just prior to exercise to post exercise.	SAC [2]
2.44	Analysis	Non-Standard EFF_F10	Mean (95% CI) Plot of Percent Change from Saline for Vc	Vc has means at Day 5 for each treatment and a follow-up. The bars represent the mean percent change from just prior to exercise to post saline infusion.	SAC [2]
Ventilatory Efficiency					
2.45-	Analysis	Non-Standard EFF_F11	Plot of VE/VCO ₂	Has 5 measures at Baseline, Day 7, and Follow-Up	SAC[2]
2.46	Analysis	Non-Standard EFF_F12	Mean (95% CI) Plot of VE/VCO ₂	Has means for each of the 5 measures at baseline, Day 7 and Follow-Up	SAC[2]
2.47	Analysis	Non-Standard EFF_F13	Plot of VE/VCO ₂ Change from Day -1	Is the difference between day -1 and day 7 for each time point in the exercise test (e.g. at rest day 7 – at rest day -1, post 1 min day 7 - post 1 min day -1)	SAC[2]

Efficacy Figures					
No.	Population	IDSL / TST ID / Example Shell	Title	Programming Notes	Deliverable [Priority]
2.48	Analysis	Non-Standard EFF_F14	Mean (95% CI) Change from Baseline Plot of VE/VCO ₂	Mean values of the points calculated for previous plot	SAC[2]
2.49	Analysis	Non-Standard EFF_F15	Plot of VE/VCO ₂ Change from Rest	Has 5 measures at baseline and Day 7 for each treatment along with follow-up. Bars represent the difference between the time measure and rest within a day and treatment. The number is the difference between the active and placebo bars.	SAC[2]
2.50	Analysis	Non-Standard EFF_F16	Mean (95% CI) Plot of VE/VCO ₂ Change from Rest	Has means at Day 7	SAC[2]
Pulmonary Function					
2.51	Analysis	Non-Standard EFF_F17	Spaghetti Plot of FVC	FVC has means at Baseline, Day 4 and Day 7 for each treatment and a follow-up measure	SAC[2]
2.52	Analysis	Non-Standard EFF_F18	Mean (95% CI) Plot of FVC	FVC has means at Baseline, Day 4 and Day 7 for each treatment and a follow-up measure	SAC[2]
2.53	Analysis	Non-Standard EFF_F19	Mean (95% CI) Plot of FVC Change from Baseline	FVC has means at Day 4 and Day 7	SAC[2]
2.54	Analysis	Non-Standard EFF_F17	Spaghetti Plot of FEV ₁	FEV ₁ has means at Baseline, Day 4 and Day 7 for each treatment and a follow-up measure	SAC[2]
2.55	Analysis	Non-Standard EFF_F18	Mean (95% CI) Plot of FEV ₁	FEV ₁ has means at Baseline, Day 4 and Day 7 for each treatment and a follow-up measure	SAC[2]

Efficacy Figures					
No.	Population	IDSL / TST ID / Example Shell	Title	Programming Notes	Deliverable [Priority]
2.56	Analysis	Non-Standard EFF_F19	Mean (95% CI) Plot of FEV ₁ Change from Baseline	FEV ₁ has means at Day 4 and Day 7.	SAC[2]
2.57	Analysis	Non-Standard EFF_F17	Spaghetti Plot of FEF ₂₅₋₇₅	FEF ₂₅₋₇₅ has means at Baseline, Day 4 and Day 7 for each treatment and a follow-up measure	SAC[2]
2.58	Analysis	Non-Standard EFF_F18	Mean (95% CI) Plot of FEF ₂₅₋₇₅	FEV ₂₅₋₇₅ has means at Baseline, Day 4 and Day 7 for each treatment and a follow-up measure	SAC[2]
2.59	Analysis	Non-Standard EFF_F19	Mean (95% CI) Plot of FEF ₂₅₋₇₅ Change from Baseline	FEF ₂₅₋₇₅ has means at Day 4 and Day 7	SAC[2]
2.60	Analysis	Non-Standard EFF_F17	Spaghetti Plot of FEF ₅₀	FEF ₂₅₋₇₅ has means at Baseline, Day 4 and Day 7 for each treatment and a follow-up measure	SAC[2]
2.61	Analysis	Non-Standard EFF_F18	Mean (95% CI) Plot of FEF ₅₀	FEF ₅₀ has means at Baseline, Day 4 and Day 7 for each treatment and a follow-up measure	SAC[2]
2.62	Analysis	Non-Standard EFF_F19	Mean (95% CI) Plot of FEF ₅₀ Change from Baseline	FEF ₅₀ has means at Day 4 and Day 7.	SAC[2]
2.63	Analysis	Non-Standard EFF_F17	Spaghetti Plot of FEF ₇₅	FEF ₇₅ has means at Baseline, Day 4 and Day 7 for each treatment and a follow-up measure	SAC[2]
2.64	Analysis	Non-Standard EFF_F18	Mean (95% CI) Plot of FEF ₇₅	FEF ₇₅ has means at Baseline, Day 4 and Day 7 for each treatment and a follow-up measure	SAC[2]

Efficacy Figures					
No.	Population	IDSL / TST ID / Example Shell	Title	Programming Notes	Deliverable [Priority]
2.65	Analysis	Non-Standard EFF_F19	Mean (95% CI) Plot of FEF ₇₅ Change from Baseline	FEF ₇₅ has means at Day 4 and Day 7.	SAC[2]
2.66	Analysis	Non-Standard EFF_F23	Forest Plot of Pulmonary Function Test	Forest plot of FVC, FEV ₁ , FEF ₂₅₋₇₅ , FEF ₅₀ , FEF ₇₅ . Include the mean absolute change next to the box plot as seen in the mock-up	SAC[2]
Dyspnea					
2.67	Analysis	Non-Standard EFF_F17	Spaghetti Plot of Dyspnea	Dyspnea has measures at Baseline pre and post exercise, Day 5 pre-saline sitting and supine, and Day 7 pre and post exercise	SAC[2]
2.68	Analysis	Non-Standard EFF_F18	Mean (95% CI) Plot of Dyspnea	Dyspnea has means at Baseline pre and post exercise, Day 5 pre-saline sitting and supine, and Day 7 pre and post exercise.	SAC[2]
2.69	Analysis	Non-Standard EFF_F19	Mean (95% CI) Plot of Dyspnea Change from Baseline	Dyspnea has means at Baseline post exercise, Day 5 pre-saline sitting and supine, and Day 7 pre and post exercise	SAC[2]
SF-36 Score					
2.70	Analysis	Non-Standard EFF_F19	Mean (95% CI) Plot of SF-36 Acute Score Change from Baseline	SF-36 Acute Score has means at Day -1 and Day 7	SAC[2]
Respiratory Rate					
2.71	All Subject	Non-Standard EFF_F20	Individual Plot of 24-Hour Respiratory Monitoring	There will be a graph for each patient individually	SAC[2]
2.72	All Subject	Non-Standard EFF_F21	Mean (95% CI) Plot of 24 Hour Respiratory Rate Monitoring		SAC[2]

11.13.7. Safety Tables

Safety Tables					
No.	Population	IDSL / TST ID / Example Shell	Title	Programming Notes	Deliverable [Priority]
Exposure					
3.01	All Subjects	EX1	Summary of Extent of Exposure		SAC [2]
Adverse Events					
3.02	All Subjects	AE5	Summary of All Adverse Events by System Organ Class	Include total column. Exclude pre-treatment AEs and washout period AEs	SAC [2]
3.03	All Subjects	AE3	Summary of Common Adverse Events by Overall Frequency	AE is considered common if more than one subject experiences it regardless of treatment. Exclude pre-treatment AEs and washout period AEs	SAC [2]
3.04	All Subjects	AE5	Summary of Drug-Related Adverse Events by System Organ Class	Include total column. Exclude pre-treatment and washout period AEs	SAC [2]
3.05	All Subjects	AE1	Summary of Serious Adverse Events by System Organ Class		SAC [2]
3.06	All Subjects	AE1	Summary of Adverse Events Leading to Withdrawals from Study / Permanent Discontinuation of Study Treatment		SAC [2]
3.07	All Subjects	AE15	Summary of Common (>=20%) Non-serious Adverse Events by System Organ Class and Preferred Term		SAC [2]
3.08	All Subjects	AE16	Summary of Serious Adverse Events by System Organ Class and Preferred Term		SAC [2]

Safety Tables					
No.	Population	IDSL / TST ID / Example Shell	Title	Programming Notes	Deliverable [Priority]
Labs					
3.09	All Subjects	LB1	Summary of Clinical Chemistry Laboratory Values by Visit		SAC [2]
3.10	All Subjects	LB1	Summary of Chemistry Changes from Baseline by Visit		SAC [2]
3.11	All Subjects	LB3	Summary of Chemistry Results by Potential Clinical Importance Criteria		SAC [2]
3.12	All Subjects	LB2	Summary of LFTs of Potential Clinical Importance by Visit	Include ALT and total Bilirubin	SAC [2]
3.13	All Subjects	LB1	Summary of Percent Change from Baseline of LFTs by Visit		SAC [2]
3.14	All Subjects	LB1	Summary of Haematology/Coagulation Changes from Baseline by Visit		SAC [2]
3.15	All Subjects	LB17	Summary of Haematology Results by Potential Clinical Importance Criteria		SAC [2]
Vital Signs					
3.16	All Subjects	VS1	Summary of Vital Signs by Visit	Include the Respiration Rate and Temperature	SAC [2]
3.17	All Subjects	VS3	Summary of Change from Baseline in Vital Signs by Visit	Include the Respiration Rate and Temperature	SAC [2]
3.18	All Subjects	VS2	Summary of Vital Signs Results by Potential Clinical Importance Criteria		SAC [2]

Safety Tables					
No.	Population	IDSL / TST ID / Example Shell	Title	Programming Notes	Deliverable [Priority]
ECGs					
3.19	All Subjects	EG1	Summary of ECG Findings by Visit		SAC [2]
3.20	All Subjects	EG2	Summary of Maximum QTc Values by Category.		SAC [2]
3.21	All Subjects	EG2	Summary of Change from Baseline in ECG Values by Visit.		SAC [2]

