7.4.1.1. Time period and Frequency for collecting AE and SAE information

- AEs and SAEs will be collected from the start of Study Treatment until the follow-up contact (see Section [7.4.1.3](#)), at the timepoints specified in the Time and Events Table (Section [7.1](#)).
- Medical occurrences that begin prior to the start of study treatment but after obtaining informed consent may be recorded on the Medical History/Current Medical Conditions section of the CRF.
- Any SAEs assessed as related to study participation (e.g., protocol-mandated procedures, invasive tests, or change in existing therapy) or related to a GSK product will be recorded from the time a subject consents to participate in the study up to and including any follow-up contact.
- All SAEs will be recorded and reported to GSK within 24 hours, as indicated in [Appendix 5](#).
- Investigators are not obligated to actively seek AEs or SAEs in former study subjects. However, if the investigator learns of any SAE, including a death, at any time after a subject has been discharged from the study, and he/she considers the event reasonably related to the study treatment or study participation, the investigator must promptly notify GSK.

NOTE: The method of recording, evaluating and assessing causality of AEs and SAEs plus procedures for completing and transmitting SAE reports to GSK are provided in [Appendix 5](#)

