9.4.3. Other Analyses

Safety data will be presented in tabular and/or graphical format and summarized descriptively according to GSK's Integrated Data Standards Library (IDSL) standards. No formal statistical analyses are planned for safety data. Safety data will be listed and summarized. All subjects who received an active dose of study medication will be included in the evaluation of clinical safety and tolerability. Clinical monitoring and laboratory safety will be reviewed by the Investigator and vital signs will be summarized by treatment.

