3.3. Study Design

Overview of Study Design and Key Features	

Period I
 
Period II
 
Screening → GSK2798745 7 days or Placebo 7 days → 14-day Washout → GSK2798745 7 days or Placebo 7 days → Follow-up
 
Legend:
 
 Sleep Study (Optional) DLco (PFTs) Exercise DLco* Saliva Infusion* 
*Eligible Subjects Only
	
Design Features	
 This is a randomized, double-blind, sponsor-unblinded, placebo-controlled, 2 X 2 crossover study in adults with heart failure. The

Overview of Study Design and Key Features	
	
study will be conducted at multiple centers.
 
 Subjects have an at least 3 month history of HF, be a NYHA Class II-IV, a NT-proBNP of greater than 400 pg/ml within the last 6 months and a % predicted DLco of < 80% at screening.
Dosing	
 Subjects are dosed once daily for 7 days. Then there is a wash out period of at least 14 days, followed by another 7 days of once daily dosing.
Treatment Assignment	
 Eligible subjects will be randomized to one of two treatment sequences. A sufficient number of subjects with heart failure will be enrolled so that 12 subjects complete the two study periods and critical assessments. Subjects will receive either GSK2798745 or placebo once daily for a period of 7 days. After at least a 14-day washout period (preferably not greater than 30 days from last dose in Period I), subjects will participate in a second, identical 7-day study period and receive the alternate study medication.
Interim Analysis	
 After approximately 5-6 subjects complete both study periods, a sponsor unblinded interim analysis will be performed. After approximately 9 subjects complete both study periods, a sponsor unblinded interim analysis will be performed. After 12 subjects complete both study periods, prior to SAC, an interim analysis will be performed to determine if additional subjects will be enrolled in the study (up to 24 subjects). Full details are in Section 3.1

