11.3.3. Treatment States for AE Data

Treatment State	Definition
AE = Pre-Treatment	AE Start Date < Study Treatment Start Date
AE = On-Treatment	If AE onset date is on or after the treatment start date and on or before the treatment stop date. Study Treatment Start Date ≤ AE Start Date ≤ Study Treatment Stop Date [+ 1]
AE = Post-Treatment	If AE onset date is after the treatment stop date. AE Start Date > Study Treatment Stop Date + 1
AE Onset Time Since 1 st Dose (Days)	If Treatment Start Date > AE Onset Date : = AE Onset Date - Treatment Start Date If Treatment Start Date ≤ AE Onset Date : = AE Onset Date – Treatment Start Date + 1 Missing otherwise
AE Duration (Days)	AE Resolution Date – AE Onset Date + 1
AE = Drug-related	If relationship is marked 'YES' on [Inform/CRF OR value is missing.

NOTES:

- If the study treatment stop date is missing then the AE will be considered to be On-Treatment

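### SAP Tables 3.02 to 3.04 leave out washout AEs but not AEs after Period II, so tabulation of a post-dose AE depends on sequence and the AE tables need not reconcile

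*SAP*

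**What the plan says.** SAP 11.13.7 lists seven AE tables. The notes for Table 3.02 (all AEs) and Table 3.03 (common AEs) include "Exclude pre-treatment AEs and washout period AEs". The note for Table 3.04 (drug-related AEs) includes "Exclude pre-treatment and washout period AEs". None of the three mentions AEs that start after the last Period II dose. The notes are blank for Table 3.05 (SAEs), Table 3.06 (AEs leading to withdrawal or permanent discontinuation), Table 3.07 ("Summary of Common (>=20%) Non-serious Adverse Events by System Organ Class and Preferred Term") and Table 3.08 (SAEs by system organ class and preferred term).

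Protocol 7.4.1.1 states that "AEs and SAEs will be collected from the start of Study Treatment until the follow-up contact", so collection covers both the washout and the interval after Period II. Protocol 9.4.3 adds "Safety data will be listed and summarized" and mentions no washout exclusion.

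SAP 11.3.3 defines the AE states. The on-treatment state is worded "If AE onset date is on or after the treatment start date and on or before the treatment stop date", but the formula beside it runs to one day after the stop date. The post-treatment formula is "AE Start Date > Study Treatment Stop Date + 1". Neither is tied to a period. SAP 11.3.1 does define period-specific phases (pre-, on- and post-treatment for Periods 1 and 2), but none is called washout.

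**The concern.** In a two-period crossover, the washout is the post-dose interval for the Period I treatment, and follow-up is the post-dose interval for the Period II treatment. A rule that removes AEs from the first and says nothing about the second treats the same kind of event differently according to the sequence the subject was assigned. It does so even when the investigator has judged the event drug-related.

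It also undermines the usual check that subset tables fit inside the all-AE table. If SAEs and withdrawal AEs from the washout are counted in their own tables but not in the overall one, a reader of the study report cannot reconcile the counts. In a trial this small, one or two events can change what a table shows.

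**Working it through.** There is no planned figure to reproduce. The check applies the written notes to an AE that starts more than one day after a period's last dose.

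**Step 1: the rule by sequence.** Sequences AP and PA are those in protocol 6.2.

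| Sequence and interval | Preceding treatment | Tables 3.02 to 3.04 | Tables 3.05 to 3.08 |
|---|---|---|---|
| AP, washout | GSK2798745 | excluded | no exclusion stated |
| AP, after Period II | placebo | no exclusion stated | no exclusion stated |
| PA, washout | placebo | excluded | no exclusion stated |
| PA, after Period II | GSK2798745 | no exclusion stated | no exclusion stated |

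The sequence dependence is therefore confined to Tables 3.02 to 3.04. The failure to reconcile lies between those tables and 3.05 to 3.08.

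**Step 2: two consequences.**
- A washout SAE can enter 3.05 and 3.08, and a washout AE causing withdrawal can enter 3.06, while neither enters 3.02.
- Table 3.03 calls an AE common if more than one subject has it. One on-treatment case plus one washout case of the same term counts as one subject, so the term drops out of 3.03. The same two cases could both count towards the 20% cut-off in 3.07. The SAP does not say whether that cut-off applies to the total or to a treatment column.

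**Step 3: how many days are affected.** Inputs:
- Washout: SAP 3.3 has "After at least a 14-day washout period (preferably not greater than 30 days from last dose in Period I".
- Follow-up: 14 ± 4 days after the last dose (protocol 7.1), so day 10 to day 18.
- Post-treatment starts on day 2 after the last dose, from the SAP 11.3.3 formula.
- Assumptions: equal sequences; washout counted from the last Period I dose to the first Period II dose.

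The calculation takes one AP and one PA subject. For each, the post-active interval is the washout (AP) or follow-up (PA). Share left out = washout days / (washout days + follow-up days).
- 14-day washout, days 2 to 13 = 12 days. Day-14 follow-up, days 2 to 14 = 13 days. 12/(12 + 13) = 12/25 = 48%.
- 14-day washout, day-18 follow-up (17 days): 12/29 = 41%.
- 30-day washout (days 2 to 29 = 28 days), day-10 follow-up (9 days): 28/37 = 76%. Thirty days is only a preferred limit, so 76% is not a ceiling.
- If 14 full drug-free days are required, the washout contributes 13 days: 13/26 = 50%.

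Adding the active on-treatment days (Days 1 to 8, so 8 for each of the two subjects, 16 in all) gives 12/(25 + 16) = 12/41 = 29%. The other two combinations become 12/45 = 27% and 28/53 = 53%.

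SAP 4.1 implies 11 subjects (10 plus one more). If they split 6:5 or 5:6 between AP and PA, the 48% becomes 72/137 = 53% or 60/138 = 43%.

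**Step 4: the definitions behind the note.** A washout date satisfies both Post-Treatment 1 (after the Period 1 stop date) and Pre-Treatment 2 (before the Period 2 start date) in SAP 11.3.1. In 11.3.3 the AE states are not linked to these phases. An AE starting the day after the last dose is post-treatment by the prose and on-treatment by the formula.

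**The case against.** The strongest objection is that the sequence effect rests partly on silence. The notes do not say that AEs after Period II are tabulated; they only fail to exclude them. The tables use sponsor-standard IDSL shells, which SAP 11.4.3 applies unless otherwise stated and which are not in the documents. A shell could restrict the tables to on-treatment events, which would remove the asymmetry in 3.02 to 3.04, or could add an exclusion to 3.05 to 3.08. This stands as a condition on the conclusion. It does not explain why an explicit washout exclusion is written for three of the seven tables and for no other post-dose interval.

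A reader might infer more than the documents support:
- **That the rule hides harm from the active drug.** Washout AEs after placebo are dropped by the same note, so with balanced sequences no direction of bias is shown.
- **That the events vanish from the report.** Listing 12 covers all AEs with no stated exclusion, and washout SAEs are still summarised in 3.05 and 3.08. What can be missing from the summaries is mainly non-serious washout AEs.
- **That the SAP contradicts the protocol.** A general commitment to list and summarise safety data does not require every AE in every table.
- **That a washout AE would be classed as on-treatment.** Reading 11.3.3 over the whole study gives that result, but 11.3.1 already has period phases and the table notes treat washout AEs as a separate class. What remains is a missing cross-reference, an overlap of phases in the washout and a one-day mismatch.

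It is also fair to say that the protocol regards the 14-day washout as removing carryover, so attributing an event weeks after a 7-day course to that course is a judgement. That bears on which common rule to choose, not on whether one is needed.

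**Conclusion.** The concern holds. Unless a shell outside the documents says otherwise, the notes make tabulation of a non-serious post-dose AE in Tables 3.02 to 3.04 depend on sequence, and they allow SAEs and withdrawal AEs from the washout to sit outside the all-AE table. This is a stated rule with an inconsistent result, not merely missing detail.

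The size can be given only in observation time: 48% of post-active days in the base case (41% to 76% over the combinations shown), or 29% once on-treatment days are counted. These are not shares of AEs and should not be read as the proportion of events lost; the number of events affected cannot be derived from the documents. The figures rest on equal sequences and the day-counting convention above.

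The point should be corrected, but with no directional bias shown and the events kept in Listing 12, it does not undermine the safety data themselves.

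**What to change.** Apply one rule to AEs starting after a period's last dose, the same after both periods and in all of Tables 3.02 to 3.08. Preferably:
- delete the washout exclusion from 3.02 to 3.04;
- attribute each post-dose AE to the treatment of the preceding period;
- show on-treatment and post-treatment AEs separately, with subject-days of observation for the post-treatment column.

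At a minimum, treat washout and post-Period II AEs alike in every AE table, whether all in or all out.

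In SAP 11.3.3, index the AE states to the period phases of 11.3.1, place washout AEs in one phase only, and align the on-treatment prose with the formula that runs to one day after the stop date. If the shells already carry a phase rule, state it in the SAP.

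The cost is SAP wording and programming on data already collected. Under the preferred rule some unrelated late events will be counted, and the washout and follow-up intervals differ in length; the separate column with its observation time makes both visible.
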